**Research Aims:**

1. **Research Questions(s):** Does Intraoperative Ketamine improve quality of recovery after laparoscopic gastric reduction surgery?
2. **Hypotheses:** Intraoperative ketamine will improve postoperative quality of recovery after laparoscopic gastric reduction.

**Research significance:**

**Background:**

Laparoscopic surgery for gastric reduction is frequently associated with high levels of postoperative pain. Postoperative pain is very often treated with opioids. However large doses of opioids can result in respiratory depression with hypoxemia especially in high risk patients with obstructive sleep apnea. Since a large group of patients undergoing surgery for gastric reduction surgery also have obstructive sleep apnea, it is expected that these patients are also at high risk for postoperative respiratory depression and hypoxemia.

Intraoperative ketamine has been used as an effective multimodal agent to reduce postoperative pain. However, ketamine alone has not been examined to improve postoperative pain outcomes in patients undergoing gastric reduction surgery. More importantly, it is unknown if the use of intraoperative ketamine can lead to better overall quality of recovery in the same patient population. In addition, ketamine has been shown to improve ventilation but it remains to be determined if the intraoperative use of ketamine will result in decreased postoperative opioid use and hence less complications such as hypoxic episodes within the first 24 hours after surgery.

The main objective of the current investigation is to examine the effect of intraoperative ketamine on postoperative quality of recovery after gastric reduction

surgery. We hypothesize that subjects receiving ketamine will have a greater global quality of recovery score than the ones receiving saline (placebo group). We also seek to determine if intraoperative ketamine would decrease the incidence of postoperative opioid requirements in the same patient population.

### **Investigational Plan**

**Study design:** Randomized, double blinded placebo controlled clinical trial

#### **Methods:**

- 1. Primary outcome:** QoR-40 at 24 hours
- 2. Size of study groups(s):**  
It would be required to have 36 patients per group in order to achieve 80% power to detect a 10 point difference on the QoR-40 instrument with an estimated standard deviation of 15. To compensate for drop-outs or loss to follow-up, 80 patients will be recruited and randomized.
- 3. Secondary outcomes:**  
Postoperative opioid consumption  
Postoperative pain scores  
Length of hospital stay (Hours)
- 4. Patient entry, exclusion and dropout criteria:**  
**Entry:** Age 18-64, surgery: laparoscopic gastric reduction (gastric sleeve or gastric bypass), ASA I, II, III; BMI >35kg/m^2, Fluent in English  
**Exclusion:** History of allergy to protocol medications, History of chronic opioid use, pregnant patients.
- 5. Drop out:** Conversion to an open surgical route, patient or surgeon request.
- 6. Protocol specific methods:** Patients will be recruited on the day of surgery. Informed consent will be signed. Participant will complete the preoperative QoR-40 questionnaire (appendix 1) along with the Stop-BANG questionnaire (appendix 2). All medication except for propofol will be dosed based on the adjusted body weight (ABW=Ideal body weight (IBW) + [0.4 X (actual body weight –IBW)] Patients will be randomized using a computer generated table of random number to 2 groups: Group K (ketamine) will receive 0.5mg /kg of ketamine bolus followed by an infusion of 0.5 mg/kg/hour of ketamine throughout the intraoperative period. Group P (placebo) will receive the same amount of saline. The investigators will be blinded to study drug. The medication will be prepared by the hospital pharmacy and is not involved with the case or data collection.  
Subjects will be premedicated with midazolam (0.02-0.04 mg/kg IV preoperatively. Routine ASA monitors will be applied. Anesthesia will be induced with remifentanyl infusion started at 0.1 mcg/kg/minute titrated to keep blood pressure within 20% of the baseline and propofol 1.5 -2.5 mg/kg. Tracheal intubation will be facilitated with succinylcholine (1-2 mg /kg). Anesthesia will

be maintained with sevoflurane titrated to a bispectral index (BIS) between 40-60, remifentanyl infusion started at 0.1mcg/kg/min titrated to keep blood pressure within 20 % of baseline values, and neuromuscular blockade will be maintained with rocuronium that will be administered at the discretion of the anesthesiologist. Upon termination of the surgery, residual neuromuscular blockade will be antagonized with a combination of neostigmine 0.05mg/kg (to a maximum dose of 5mg) and glycopyrrolate 0.01 mg/kg . Remifentanyl will be discontinued at the time of the removal of the laparoscope from the abdomen and hydromorphone 10 mcg/kg IV will be administered. Ondansetron 4 mg IV and dexamethasone 4 mg IV will be administered to prevent postoperative nausea and vomiting. Study drug will be discontinued at the end of the surgical procedure as the dressings are being placed. Normothermia will be maintained intraoperatively using a forced air warming blanket (Bairhugger, Arizant healthcare INC, Eden Prairie, MN). Subjects will receive IV Hydromorphone in divided doses as needed to achieve a verbal rating score for pain <4 out of 10 starting in the operating room following extubation and in PACU. Metoclopramide (10 mg IV) will be used as rescue antiemetic. Patient-controlled analgesia, programmed to deliver 0.2 mg of hydromorphone every 10 minutes, will be instituted before the patient is discharged from the PACU. Before PACU discharge, the LSD ARCI questionnaire (appendix 3) will be completed by the patient to assess for other untoward effects of ketamine. Ketorolac 30 mg every 6 hours for 24 hours will be started when admitted to patient room. SpO2 will be monitored continuously for 24 hours after discharge from PACU. At 24 hours after surgery patients will complete the QoR-40 (appendix 1) instrument.

**Risks/Benefits:** Participants may not have any direct benefit from taking part in this study. Taking part in this study may help us determine whether the study drug increases 24 hour quality of recovery and decreases opioid requirements within 24 hours of the surgery.

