#### **Most Frequent:**

Delirium  
Hallucinations  
Mood changes  
Nightmares  
Tachyarrhythmia  
Tonic- Clonic Epilepsy  
Vocalization

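### The drop-out rule reads as removing randomised patients from the QoR-40 comparison, and no as-randomised analysis is stated

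*Combined protocol and SAP*

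**What the plan says.** Methods item 5 (Drop out) reads in full: "Conversion to an open surgical route, patient or surgeon request". It does not say what happens to these patients' data.

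Methods item 2 (Size of study groups) requires 36 patients per group for 80% power to detect 10 points with a standard deviation of 15. It then says: "To compensate for drop-outs or loss to follow-up, 80 patients will be recruited and randomized". Drop-outs are named separately from loss to follow-up.

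Methods item 6 (Protocol specific methods) says of the primary outcome: "At 24 hours after surgery patients will complete the QoR-40 (appendix 1) instrument". It does not say whether drop-outs are included. The same item collects a baseline score: "Participant will complete the preoperative QoR-40 questionnaire (appendix 1) along with the Stop-BANG questionnaire".

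The supplied text states no analysis set, no analysis by assigned group and no rule for missing scores. The Research Aims and the entry criteria refer to laparoscopic surgery, whereas the main objective under Background is broader: "to examine the effect of intraoperative ketamine on postoperative quality of recovery after gastric reduction".

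**The concern.** A patient has to be compensated for in the sample size only if that patient contributes nothing to the comparison. Listing drop-outs beside loss to follow-up suggests that they are set aside even when they could be reached at 24 hours. Every listed reason can arise after randomisation and after study drug has started.

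Post-randomisation removal biases the estimate when two things hold together: the probability of removal depends on treatment, and removed patients recover differently from those who stay. A chance imbalance in counts does no harm.

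Nothing in the documents suggests that ketamine affects open conversion. A request to leave is the more plausible route. The list of most frequent ketamine side effects includes delirium, mood changes and "Hallucinations". Before PACU discharge a questionnaire "will be completed by the patient to assess for other untoward effects of ketamine". The QoR-40 itself scores bad dreams, anxiety, depression and confusion. A ketamine patient who leaves because of such effects would probably have been a low scorer, and the removal would favour ketamine. Without a stated rule, the decision on whom to exclude could also be made after scores are seen.

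**Working it through.** **Inputs from Methods item 2.** Difference 10, SD 15, power 80%, 36 per group, 80 randomised. Assumed because not stated: two-sided alpha 0.05 and 1:1 allocation (40 per arm).

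**Reproducing the plan's figures.** n = 2 × (15/10)² × (1.960 + 0.842)² = 35.3, rounded up to 36 per group. A one-sided 0.05 test would need 28, so two-sided 0.05 fits. Then 72/(1 − 0.10) = 80, an allowance of 10%. By the t-test, power is 79.7% at 36 per arm and 83.8% at 40 per arm.

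**Bias formula.** Let pK and pP be the proportions removed in the ketamine and placebo arms because of treatment, and let gap be the number of points by which removed patients score below those retained. With no true difference among all randomised patients, the retained-patient difference is shifted by

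shift = (pK − pP) × gap.

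The false-positive rate comes from the noncentral t distribution with nc = shift / (15 × √(1/n1 + 1/n2)), where n1 and n2 are the numbers retained. Worked case, 6 v 2 removed and gap 30: shift = (0.15 − 0.05) × 30 = 3; standard error = 15 × √(1/34 + 1/38) = 3.54; nc = 0.85; rejection 13.3%.

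The removal rates and gaps below are assumptions; the documents give none.

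| Removed of 40 (ketamine v placebo) | Shift at gap 10 / 20 / 30 | False-positive rate |
|---|---|---|
| 2 v 0 (5% v 0%) | 0.5 / 1.0 / 1.5 | 5.2% / 6.0% / 7.2% |
| 5 v 3 (12.5% v 7.5%) | 0.5 / 1.0 / 1.5 | 5.2% / 5.9% / 7.0% |
| 6 v 2 (15% v 5%) | 1 / 2 / 3 | 5.9% / 8.6% / 13.3% |

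**Simulation check** (200,000 trials per case, 40 per arm, SD 15, no difference among all randomised). Removal of 15% v 5% gave shifts of 1.00 / 2.01 / 3.00 and rejection of 5.9% / 8.7% / 13.3%. Removal of 10% in both arms gave a shift within 0.02 of zero and rejection of 4.9% to 5.0%. The same trials analysed as randomised with all scores rejected in 4.9% to 5.0%.

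**Is the condition really 'only if'?** In a separate simulation (6,000 trials per case) with a true effect of 10, removing 8 patients at random from one arm gave 9.96, and removing the lowest 4 in each arm gave 10.07. Neither shifted the estimate. Removing 6 v 2 from the lower half of each arm gave 11.47. Two qualifications apply:

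- Trimming exactly the 4 lowest scores in each arm leaves the difference unbiased but raises rejection under no effect to 8.2%, because the trimmed spread understates the standard error.
- If the effect differs in removed patients, removal unrelated to arm changes the target. For example, 10 points in the retained 90% and 0 in the other 10% means 0.9 × 10 + 0.1 × 0 = 9 points in all randomised. That creates no false effect where there is none.

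**The case against.** - **The text never says drop-outs are excluded from analysis.** Inflating 72 to 80 is ordinary practice and also fits an as-randomised analysis with some scores missing. This stands as a limit on certainty: the defect is a rule that reads one way and is never clarified.
- **Open conversion has no shown link to treatment.** The design is "Randomized, double blinded placebo controlled clinical trial", and setting converted cases aside may be a deliberate choice of population, since the aims specify laparoscopic surgery. This also stands, but the plan does not declare such a choice and its main objective is worded more broadly.
- **The remedy is weakest where bias is most plausible.** Study drug stops at the end of surgery, so a patient who asks to leave afterwards is likely to be refusing data collection, and those scores stay missing. A baseline score cannot capture a reaction on emergence. This is largely right. The rule recovers mainly converted patients and requests made without withdrawal of consent, and reporting drop-outs by arm and reason at least exposes the rest.
- **The magnitude is assumed.** The 13.3% needs a 10-percentage-point excess caused by ketamine and a 30-point deficit, two planned SDs. The protocol also says side effects are uncommon in its dose range. Both points are fair, and the milder rows are the more likely ones.

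**Conclusion.** The concern holds as a point that should be fixed, with medium confidence. Followed as written, the plan most naturally drops randomised patients from the primary comparison for post-randomisation reasons, and it states no analysis by assigned group. Any bias is conditional and probably modest: 0.5 to 1.5 points for a 5-percentage-point treatment-caused excess of removals and 1 to 3 points for a 10-point excess, against a planned difference of 10. These figures assume that removed patients score 10 to 30 points lower, SD 15, two-sided alpha 0.05 and no true difference. Actual size and direction cannot be determined from the documents. If removal is unrelated to arm, no false effect arises.

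**What to change.** Keep the item 5 list as reasons for coming off protocol, and add: *All randomised patients are analysed in their assigned group; the 24-hour QoR-40 is still collected after open conversion or a patient or surgeon request, unless the patient withdraws consent to data collection.* Also:

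- report drop-outs by arm and reason;
- prespecify, before unblinding, a missing-score method that uses arm and the baseline QoR-40 already collected;
- report the analysis without converted or off-protocol patients as a sensitivity analysis.

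The cost is a short addition to the text and a few more questionnaires. Patients who withdraw consent to data collection stay missing.

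The SD may widen. If 15 describes completers only and a fraction f of patients score lower by the gap, the SD is √(225 + f(1 − f) × gap²). With f = 0.10 and gaps of 10 / 20 / 30, that is 15.30 / 16.16 / 17.49, and power at 40 per arm is 82.3% / 78.1% / 71.4%. This compares with 79.7% at 36 per arm after removal, or 83.8% at 40 per arm if the SD stays 15. With f = 0.05, power is 83.0% / 80.7% / 77.0%. The change is made for validity; no gain in power is claimed and no larger sample is proposed.

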**Normal Saline (placebo):**

Hypernatremia

These side effects are uncommon with the lower dose range used in this study.

There is a risk of loss of confidentiality even though there are strict measures in place to prevent occurrence. Answering some of the questionnaires or surveys may make subject feel uncomfortable. The subject may skip to the next question if the question upsets them. There is a very slight risk of skin irritation from the pulse oximeter (Konica Minolta).

**Confidentiality:** Subjects' identity will be guarded by assigning a numerical code which is only known by the principal investigator and research coordinator. Data will be stored in department computer which is password protected. Each study subject will be assigned a study code number. The code will be used to link study data to patient identification (name) in a separate database. Subject data will be stored on secure computers at Northwestern University. Data access will be password protected and only available to study investigators. The data forms will be de identified after the chart review prior to analysis. 7 years post manuscript completion the data both electronic and paper will be destroyed using current departmental approved methods of destruction.

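### The preoperative QoR-40 is collected but given no analytic role, and no primary analysis is named; pre-specified ANCOVA on it would probably add precision

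*Combined protocol and SAP*

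**What the plan says.** Methods item 1 of the combined protocol and SAP gives the primary outcome as "QoR-40 at 24 hours", with no summary measure or test attached. Item 2 sizes the trial at 36 per group for "80% power to detect a 10 point difference on the QoR-40 instrument with an estimated standard deviation of 15", and randomises 80 to allow for losses. Alpha, sidedness and the kind of SD (raw, change-score or residual) are not stated.

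Item 6 has the same instrument completed twice. On the day of surgery, "Participant will complete the preoperative QoR-40 questionnaire (appendix 1) along with the Stop-BANG questionnaire (appendix 2". Later, "At 24 hours after surgery patients will complete the QoR-40 (appendix 1) instrument".

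The Background section gives the hypothesis as "subjects receiving ketamine will have a greater global quality of recovery score than the ones receiving saline", without mentioning baseline or change. The risk text after the side-effect lists adds, about questionnaires: "The subject may skip to the next question if the question upsets them".

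The available text has no statistical analysis section. It does not use the preoperative score as a covariate, as the start point of a change score, or as a descriptive variable, and it has no rule for missing items.

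**The concern.** When one instrument is measured before and after treatment, three primary analyses are available: the 24-hour score alone, the change from the preoperative score, and the 24-hour score adjusted for the preoperative score (ANCOVA). They have different power and can give different p-values on the same data. The plan commits to none of them. The unadjusted comparison is implied only by the sample size.

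Two things are at stake. First, the choice can be made after the results are seen. Second, a trial planned at about 80% power may leave unused a covariate that it is already collecting and that could narrow the confidence interval without more patients.

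Validity is not in question. An unadjusted comparison of randomised groups is unbiased, and its standard error already covers chance baseline imbalance.

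**Working it through.** **Inputs from the plan (Methods item 2):** difference 10, SD 15, power 80%, 36 per group, 80 randomised (40 per group if split equally).

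**Assumptions:** two-sided alpha 0.05; 15 is the raw SD of the 24-hour score; the correlation r between the preoperative and 24-hour totals is unknown and shown over a range.

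**1. Reproduce the stated size.**
- Two-sided 5%: n = 2 × (1.960 + 0.842)² × (15/10)² = 35.3, so 36 per group. This matches the plan.
- One-sided 5%: n = 2 × (1.645 + 0.842)² × (15/10)² = 27.8, so 28 per group. This does not match.

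The plan's figure is thus that of an unadjusted two-sample comparison and takes no credit for the preoperative score. By the noncentral t distribution, its power is 79.7% at 36 per group and 83.8% at 40 per group.

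**2. ANCOVA at the same size.** The residual SD is 15 × √(1 − r²), with 2n − 3 degrees of freedom. The variance of the treatment difference is multiplied by 1 + 1/(2n − 4) for expected chance imbalance in the covariate. At n = 36 that factor is 1 + 1/68 = 1.0147.

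Example, r = 0.5 and n = 36: residual SD = 15 × √0.75 = 12.99; standard error = 12.99 × √(2/36) × √1.0147 = 3.084; 95% half-width = 1.995 × 3.084 = 6.15. Unadjusted: standard error = 15 × √(2/36) = 3.536; half-width = 1.994 × 3.536 = 7.05.

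| Analysis | Power, 36 per group | Power, 40 per group | 95% CI half-width, 36 per group |
|---|---|---|---|
| Unadjusted | 79.7% | 83.8% | 7.05 |
| ANCOVA, r = 0 | 79.1% | 83.3% | 7.10 |
| ANCOVA, r = 0.1 | 79.5% | 83.6% | 7.07 |
| ANCOVA, r = 0.2 | 80.7% | 84.7% | 6.96 |
| ANCOVA, r = 0.3 | 82.7% | 86.6% | 6.78 |
| ANCOVA, r = 0.5 | 89.2% | 92.2% | 6.15 |
| ANCOVA, r = 0.7 | 97.2% | 98.4% | 5.07 |

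The two analyses have equal power at r = 0.122 (36 per group) or 0.115 (40 per group). The worst case, r = 0 at 36 per group, costs 79.7 − 79.1 = 0.6 percentage points.

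**3. Change score, for contrast.** With equal SDs at both times (assumed), the SD of the change is 15 × √(2(1 − r)). At r = 0.3 this is 17.75, and power at 36 per group is 65.5%, against 79.7% unadjusted and 82.7% for ANCOVA. The choice left open therefore has real consequences even at a low correlation.

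**4. Missing preoperative totals.** Subjects may skip questions, so some totals could be incomplete. If 4 of 36 per group (assumed) were dropped for that reason, ANCOVA on 32 per group at r = 0.3 would have 77.9% power, below the unadjusted 79.7% on all 36. In simulation, with 10% of baselines missing completely at random (assumed) and filled by the overall baseline mean, power stays at about 82% and type I error at about 5%.

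**The case against.** The strongest objection is that the benefit rests on a correlation the documents do not supply, and there is some reason to expect a low one. The form asks about the previous 24 hours, and many of its items (vomiting, shivering, sore throat, severe pain) are things surgery provokes. Patients may vary little on these beforehand. At r = 0.2 the gain is one percentage point of power, and the half-width moves only from 7.05 to 6.96. This stands as a limit on the size of the gain. It does not overturn the recommendation, because the loss is at most 0.6 points if the correlation is nil.

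Second, naming an unadjusted comparison would also close the post-hoc choice, and the hypothesis, the outcome and the sample size all point that way. This is true. The argument from pre-specification requires that an analysis be named; it is the efficiency argument that favours ANCOVA.

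Third, replacing a whole total by the mean because one item was skipped discards the items that were answered. The form also asks patients to check that every question is answered, so gaps may be few. Both remarks are fair. An item-level rule would be a reasonable refinement; the mean is only a simple example that keeps every patient in the model. The simulated figure also assumes that missingness is unrelated to the scores, whereas the protocol describes skipping because a question upsets the subject. Incomplete 24-hour totals need a rule too, but that is a separate matter.

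**Conclusion.** The concern holds, as a gap in pre-specification and efficiency and not as an error in the sample size. It is firm that the preoperative QoR-40 has no stated use and that no primary analysis is named. That ANCOVA would add precision is probable, not certain: it needs r above about 0.12. At 36 per group the gain is 3.0 points of power at r = 0.3 (82.7 − 79.7) and 9.5 points at r = 0.5 (89.2 − 79.7). These figures rest on a two-sided 5% level, on 15 being the raw 24-hour SD, and on few patients being lost to an incomplete baseline. If 15 is already a residual SD, the gain does not apply. The change should be made; confidence in the size of the benefit is medium.

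**What to change.** - **Primary analysis:** ANCOVA of the 24-hour QoR-40 total on treatment group, with the preoperative QoR-40 total as covariate. Report the adjusted mean difference with a two-sided 95% confidence interval, at alpha 0.05.
- **Sensitivity analysis:** the unadjusted difference in 24-hour totals.
- **Missing baseline:** impute incomplete preoperative totals without regard to treatment group, for example by the overall baseline mean, so that no randomised patient is dropped for a missing covariate.
- **Sample size text:** state whether the SD of 15 is the raw SD of the 24-hour score, and give the alpha and sidedness used. Keep 80 randomised.

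The cost is two or three sentences of analysis wording and no new data. The model spends one degree of freedom and a small imbalance penalty, together worth at most about 0.6 percentage points of power.

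### No blocking, stratification or adjustment for operation is described for 80 patients having sleeve or bypass; adding all three is a cheap gain in precision, not the repair of a power defect

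*Combined protocol and SAP*

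**What the plan says.** Everything relevant stands in the Methods section of the combined protocol and SAP.

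- **Item 2 (size of study groups):** "It would be required to have 36 patients per group", to give "80% power to detect a 10 point difference on the QoR-40 instrument with an estimated standard deviation of 15". The significance level and its sidedness are not stated. To cover losses, "80 patients will be recruited and randomized"; no drop-out rate is given.
- **Item 4 (entry criteria):** surgery is "laparoscopic gastric reduction (gastric sleeve or gastric bypass". The expected split between the two operations is not given.
- **Item 6 (protocol specific methods):** patients are recruited on the day of surgery, and "Patients will be randomized using a computer generated table of random number to 2 groups". The hospital pharmacy prepares the study drug and takes no part in the case or in data collection.

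The text gives no allocation ratio (1:1 is implied by the equal group sizes), no block scheme, no fixed number per arm and no stratification factor. It describes no analysis that takes operation into account. It also does not say that allocation is unrestricted.

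**The concern.** The natural reading of a bare random-number table is simple randomisation, which controls neither the arm sizes nor how the two operations fall between the arms. The sample size is stated per group, and the 8 spare patients (80 - 72) are meant to cover drop-out. Uneven allocation would use up part of that cushion.

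Operation type is the one source of surgical variation that the entry criteria name. If it predicts QoR-40, opioid use or length of stay, leaving it out of both the list and the model gives away precision. It also leaves a small trial open to the remark that one arm had more of one operation. Patients are randomised on the day of surgery, so the planned operation should be known in time to use it.

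**Working it through.** **Inputs.** From Methods item 2: difference 10, SD 15, power 80%, 36 per group, 80 randomised. Assumed: two-sided 5%, 1:1 allocation, a bypass share of 30-50% and a difference between operations of 5-10 QoR-40 points. The last two have no source in the documents.

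**1. The plan's own figure.** n = 2 × SD² × (1.960 + 0.842)² / difference² = 2 × 225 × 7.85 / 100 = 35.3, so 36 per group. A one-sided 5% test would give 28, so two-sided 5% is the level that reproduces the plan. Power at 36/36 is 80.7% by the normal formula and 79.7% by the noncentral t. The t figures are used below.

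**2. Arm sizes under simple allocation.** With X ~ Binomial(80, 0.5), P(36 ≤ X ≤ 44) = 68.6%. An arm therefore starts below 36 with probability 31.4%. The central 95% range for one arm is 31 to 49.

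**3. What that costs.** Noncentrality = 10 / [15 × √(1/n₁ + 1/n₂)], with n₁ + n₂ - 2 degrees of freedom and 80 evaluable patients:

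| Split | Power |
|---|---|
| 40/40 | 83.8% |
| 36/44 | 83.4% |
| 35/45 | 83.2% |
| 31/49 | 81.8% |
| 28/52 | 80.2% |

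Power falls below 80% only if an arm has fewer than 28 patients, which has probability 0.5%. Averaged over binomial splits, power is 83.3% against 83.8% for 40/40 with 80 evaluable, and 79.1% against 79.7% for 36/36 with 72 evaluable.

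**4. Does blocking secure 36 evaluable per arm?** Probability that both arms keep at least 36, under an assumed independent drop-out rate:

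| Drop-out | Simple | Fixed 40/40 |
|---|---|---|
| 2.5% | 56.6% | 99.4% |
| 5% | 42.4% | 90.6% |
| 10% | 14.7% | 39.6% |

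Blocking helps but does not guarantee it.

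**5. Operation mix under simple allocation (simulation).** With 30-50% bypass, the bypass share differs between arms by at least 20 percentage points in 5-8% of trials if the number of bypass patients itself varies. With that number fixed at 24 or 40 of 80, the figure is about 6-9%. Equal arms alone do not remove this: at 40/40 without strata and with the same fixed numbers, it is about 9-12%. A 20-point imbalance moves that trial's unadjusted estimate by 0.20 × 5 = 1 to 0.20 × 10 = 2 points. The standard error at 36/36 is 15 × √(2/36) = 3.5 points.

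**6. Gain from using operation.** Take 15 as the SD of the mixed population. Residual SD = 15 × √[1 - p(1 - p)Δ²/225], where p is the bypass share and Δ the difference between operations:

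- p = 0.3, Δ = 5: 15 × √(1 - 0.21 × 25/225) = 14.8
- p = 0.5, Δ = 10: 15 × √(1 - 0.25 × 100/225) = 14.1

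With 69 degrees of freedom, power at 36/36 rises from 79.7% to 80.6% and 84.1% respectively. Adjustment after an unstratified 36/36 list gives 80.0-83.6%, so stratifying contributes about 0.5 points. If operation is not prognostic, the stratified and adjusted analysis loses one degree of freedom: 79.66% becomes 79.64%, a loss of 0.02 points.

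**The case against.** Simple randomisation of 80 patients is valid, and it has no end-of-block predictability, so choosing it is a defensible trade-off. Four arguments against the point deserve an answer.

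- **Thirty-six is not a floor.** A reader might infer that an arm of 35 breaks the plan's requirement or leaves the trial underpowered. Item 2 gives 36 per group as the number that yields 80% power in a balanced comparison. The table of splits shows that power depends mainly on the total and hardly on the split. This stands in full.
- **The method is not stated to be unrestricted.** A computer-generated list can be blocked. The text supports only that no restriction is described. This stands; if blocks were intended, the protocol should say so.
- **Chance imbalance is not bias.** A reader might infer that an uneven operation mix confounds the ketamine effect. Randomisation protects the comparison on average, and if 15 is the SD of the mixed population, the standard error already allows for the imbalance. This stands; what is lost is precision and the persuasiveness of the single result.
- **The prognostic effect is undocumented.** The background and hypotheses treat gastric reduction as one population, and nothing shows that the operations differ in recovery. This stands as a limit on size. It does not remove the point, because the cost when operation is irrelevant is close to nil.

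**Conclusion.** The point holds as a modest, low-cost improvement. The protocol describes no blocking, stratification or adjustment for operation while enrolling two operations.

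- **Arm sizes:** if allocation is simple, there is a 31% chance that an arm starts below 36, at an average cost of about 0.5 points of power. Drop-out matters far more to the number evaluable than the split does.
- **Operation:** stratifying and adjusting is worth about 1 to 4 points of power at 36 per arm (79.7% to about 81-84%). This rests on an assumed difference of 5-10 points, an assumed bypass share of 30-50%, a two-sided 5% test and 15 as the overall SD. The adjustment has to be in the model for the gain to be realised. It supplies nearly all of it when the difference is 10 points; when it is 5 points, the whole gain is only about 1 point.

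The documents do not support the stronger claims that the trial is underpowered by its allocation method, that the comparison would be biased, or that a blocked list would secure 36 evaluable patients in each arm.

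**What to change.** In Methods item 6, state that allocation is 1:1 from a computer-generated permuted-block list with randomly varying block sizes not disclosed to the investigators, stratified by planned operation (sleeve or bypass) and held by the hospital pharmacy. State that the primary QoR-40 analysis includes planned operation as a factor. If a blocked list already exists, describe it and add the factor to the model.

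Unfinished blocks in two strata can leave the arms slightly uneven: with a largest block of b, the arms differ by at most b/2 in each stratum, so by at most b in total. A largest block of 8 or fewer keeps the smaller arm at 40 - 8/2 = 36 or more at randomisation.

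The cost is two or three sentences and a new pharmacy list, with no extra patients or staff. The downsides are one degree of freedom and slight predictability near the end of a block, which the varying block sizes and the pharmacy-held list limit. The list should be in place before enrolment; later adjustment can recover precision but cannot restore balance.
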